## 5.3 Screening and Monitoring Evaluations and Measurements

#### 5.3.1 Medical Record Review

The following variables will be abstracted from the medical chart.

• Date of birth

- Weight
- Height
- Blood pressure
- Pulse
- Temperature
- SpO2 (Pulse Oximetry)
- Zip code of residence
- Gender
- Race/Ethnicity
- BMI
- Pulmonary function test results
- Asthma-related healthcare utilization (hospital, emergency, urgent care visits)

## 5.3.2 Physical Examination

No physical exam outside of usual care will be conducted in this study.

### 5.3.3 Vital Signs

Weight will be measured with a standardized scale.

Height will be measured with a standardized stadiometer.

Blood pressure, pulse, temperature and SpO2 will be measured by clinic staff using standard clinical procedures and equipment. This information will be abstracted from the medical record by study staff.

Pulmonary function will be measured using a Morgan Scientific spirometer.

### 5.4 Efficacy Evaluations

### **Primary Outcome:**

1. Asthma Control

### **Secondary Outcomes:**

- 1. Asthma Symptom Days
- 2. School Attendance

3. Utilization of ED/Hospital for Asthma

### 5.4.1 Diagnostic Tests, Scales, Measures, etc.

### **Primary Outcome:**

• **Asthma control** will be measured with Juniper's Asthma Control Questionnaire at baseline, 3 month, 6 month, 9 month and 12 month study visits. We will assess for changes in the ACQ scores from enrollment to completion of the study.

### Secondary Outcomes:

- **Asthma Symptoms** will be measured using a 2 week recall diary at the baseline, 3 month, 6 month, 9 month and 12 month study visits.
- School Absences will be measured by school and parental report
- **ED visits and hospitalizations** for an asthma-related cause (ICD-9 493.XX) in the 12 months preceding the start of the study and the 12 months subsequent to study initiation, abstracted from the Epic medical record. We will assess for changes in ED and hospitalization usage following study enrollment.

### 5.5 Safety Evaluation

Adverse event reports will be collected at each visit. These reports will be reviewed at weekly meetings by the PI to determine if they are a result of the study.

The Funding agency will assemble a DSMB to oversee safety of the interventions.

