### 3.3 Study Duration, Enrollment and Number of Sites

### 3.3.1 Duration of Study Participation

The study duration per subject will be up to 24 months, if participant has not completed the assigned study interventions within the first 12 months of participation.

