### 4.2 Study Treatment Phase

### 4.2.1 Study Visit 1 (Enrollment)

All study participants will complete the following:

- Consent/Assent
- Baseline Questionnaire
- Clinical and vital sign measurements of child [weight, height, BMI, blood pressure, pulse, temperature, pulse oximetry (SpO2)]
- Pulmonary function test (spirometry) with child if not obtained from medical record
- 2-week parental recall of symptoms, school absences, and work days missed
- Asthma Control Questionnaire
- Child Asthma Risk Assessment Tool (CARAT)
- Caregiver's Quality of Life Questionnaire
- Caregiver Needs Assessment
- Cost Analysis Parent Questionnaire
- Observe MDI technique and complete MDI Checklist
- Assess possible adverse events from date of enrollment

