# 4.2.2 Study Visits 2, 3, and 4 (Primary Care Office Visits)

Primary Care office visits will be scheduled for 3, 6 and 9 months post study enrollment. All study participants will complete the following:

- Asthma Control Questionnaire
- Clinical and vital sign measurements of child [weight, height, BMI, blood pressure, pulse, temperature, pulse oximetry (SpO2)]
- Pulmonary function test (spirometry) with child if not obtained from medical record.
- 2-week parental recall of symptoms, school absences, and work days missed
- Cost Analysis Parent Questionnaire
- Assess possible adverse events
- Review child's medical record for utilization of healthcare services
- Review care coordination goals and direct to community resources

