### 4.2.3 Study Visit 5 (12-Month Follow-Up)

All study participants will complete the following:

- Pulmonary function test (spirometry) with child if not obtained from medical record.
- Clinical and vital sign measurements of child [weight, height, BMI, blood pressure, pulse, temperature, pulse oximetry (SpO2)]
- 2-week parental recall of symptoms, school absences, and work days missed
- Asthma Control Questionnaire
- Caregiver's Quality of Life Questionnaire
- Cost Analysis Parent Questionnaire
- Child Asthma Risk Assessment Tool (CARAT)
- Administer Asthma Knowledge Quiz
- Observe MDI technique and complete MDI Checklist

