# 4.3.6 Home Visit 4 (12-Month Follow-Up)

- Follow-up environmental assessment
- Take photographs of child's bedroom and home's main living area (environmental remediation assessment)
- Administer Asthma Knowledge Quiz

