# 4.6 Subject Completion/Withdrawal

Subjects may withdraw from the study at any time without prejudice to their care. They may also be discontinued from the study at the discretion of the Investigator for lack of adherence to study procedures. It will be documented whether or not each subject completes the clinical study. If the Investigator becomes aware of any serious, related adverse events after the subject completes or withdraws from the study, they will be recorded in the source documents and on the CRF.

Subjects who become a ward of the state during study participation will continue to have their medical records reviewed, but will no longer participate in study visits or the completion of questionnaires. The state agency assigned legal guardianship of the participant will be asked to provide consent for medical record review of the participant during the study follow-up period. If consent cannot be obtained the participant will be withdrawn.

In the event that a parent or legal guardian regains custody and a participant is no longer a ward of the state, the legal guardian may be approached to provide consent for study participation. Once consent has been obtained, study visits can resume for the duration of the follow-up period.

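### Adverse events are to be collected at every visit, but the visit lists stop asking after month 9 and ask P+ children 7 times against 4 in P-

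*Protocol*

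**What the plan says.** The general rule is in Protocol section 5.5, repeated in the synopsis under Safety Evaluations: "Adverse event reports will be collected at each visit". Section 8.1 says events are monitored for the whole study, and section 5.1 says forms are filled in when needed during participation.

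The visit lists read as follows:

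- Section 4.2.1 (Visit 1, all children): "Assess possible adverse events from date of enrollment".
- Section 4.2.2 (Visits 2 to 4): "Primary Care office visits will be scheduled for 3, 6 and 9 months post study enrollment. All study participants will complete the following". The list that follows includes "Assess possible adverse events".
- Sections 4.3.2 to 4.3.4 (Home Visits 1 to 3, due within 2, 4 and 6 weeks): the same item each time, plus a chart review for utilization.
- Sections 4.2.3 (Visit 5, all children), 4.3.6 (Home Visit 4) and 4.3.7 (Visit 6): no adverse event item. Visit 5 also lacks the chart review listed at Visits 2 to 4.
- Table 1: no adverse event row.

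Under section 3.1, P- children get no home visits in their first year. On length, section 3.3.1 states: "The study duration per subject will be up to 24 months, if participant has not completed the assigned study interventions" within the first 12 months. For later events, section 4.6 provides for a record only in this case: "If the Investigator becomes aware of any serious, related adverse events after the subject completes or withdraws".

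Neither document specifies a comparative analysis of adverse events. The SAP appendix reproduces the CONSORT checklist, whose item 19 asks for harms by group. Protocol section 6.4 and SAP section 5.3 both say that reporting will follow CONSORT.

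**The concern.** The general rule and the lists cannot both describe what a site does. If staff work from the lists, two things follow.

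First, scheduled questioning ends at month 9, although the primary endpoint is read at month 12 and some children may still be receiving interventions after that. The weekly review of reports by the principal investigator and the reporting to the DSMB can only use what was collected.

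Second, the child-level arms are asked on different schedules. P+ caregivers are asked three times in the first 6 weeks. P- caregivers are first asked after enrollment at month 3. If caregivers forget minor events, a by-group harms table could show more in P+ with no true difference. No rule says which assessments feed such a table.

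**Working it through.** The plan gives no figure to reproduce here. The check is a count from the lists, then an illustration of how far unequal questioning could matter.

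**1. Count of listed questions**

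| Visit | Time | P+ | P- |
|---|---|---|---|
| Visit 1 | enrollment | 1 | 1 |
| Home Visits 1, 2, 3 | within 2, 4, 6 weeks | 3 | – |
| Visits 2, 3, 4 | months 3, 6, 9 | 3 | 3 |
| Visit 5 | month 12 | 0 | 0 |
| Home Visit 4 | month 12 | 0 | – |
| Visit 6 | after month 12 | 0 | – |
| Total | | 7 | 4 |

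The ratio is 7/4 = 1.75. After enrollment it is 6 against 3. From enrollment up to and including month 3 it is 4 against 1; from month 3 to month 9 the arms are asked equally. Visit 6 is counted in P+ only, because section 4.3 lists it under the primary care intervention. No listed question depends on S+ or S-.

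**2. Time without a scheduled question**

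Months 9 to 12 are 3/12 = 25% of the main follow-up, in both arms. At the maximum duration it is (24 − 9)/24 = 15/24 = 62.5%, but that applies only to a child whose interventions are unfinished at month 12.

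**3. Effect of unequal questioning over 12 months (illustrative)**

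Assume equal, constant true event rates, with each event reported at the next listed question with probability 2^(−lag/h), where h is a recall half-life in months. For gaps L between questions, the fraction reported over 12 months is (1/12) × Σ (1 − 2^(−L/h)) × h/ln 2. P+ is asked at weeks 2, 4 and 6 and months 3, 6 and 9; P- at months 3, 6 and 9.

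| Half-life | P+ | P- | Ratio |
|---|---|---|---|
| full recall | 0.750 | 0.750 | 1.00 |
| 6 months | 0.658 | 0.634 | 1.04 |
| 3 months | 0.582 | 0.541 | 1.08 |
| 1 month | 0.390 | 0.316 | 1.24 |
| 0.5 month | 0.257 | 0.178 | 1.45 |

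The half-lives are assumptions. The only time reference in any item is at Visit 1, which is itself the enrollment visit; the later items give none.

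**4. The first quarter alone**

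Only weeks 0 to 6 of 13 differ. After week 6 both arms wait for Visit 2. With an assumed 90% capture in P+ for weeks 0 to 6, and capture c everywhere else, the ratio is (6 × 0.9 + 7c)/(13c):

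- c = 0.8: 11.0/10.4 = 1.06
- c = 0.7: 10.3/9.1 = 1.13
- c = 0.5: 8.9/6.5 = 1.37

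**5. Two simple remedies checked**

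- Applying the each-visit rule literally gives P+ 10 questions (Visits 1 to 6 and Home Visits 1 to 4) against 5 in P-, or 6 if Visit 6 also applies there. The late gap closes, but the imbalance remains.
- Tabulating only common-visit reports, with each question covering the time since the last assessment, removes P+ events from weeks 0 to 6 but keeps those weeks in P-. With full recall and equal true rates the first-quarter ratio becomes 7/13 = 0.54, which would make the intervention look safer than it is.

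**The case against.** The strongest reply is that section 5.5 is a general rule which already covers Visit 5, Home Visit 4 and Visit 6, so three bullets were simply left out. Other routes also stay open: as-needed forms, monitoring throughout, and chart abstraction. Section 5.4.1 takes asthma-related ED visits and hospitalizations from the record for the 12 months after study initiation, section 5.3.1 adds urgent care, and the synopsis continues record review for up to two years after the 12-month visit. The indirect harm named in section 9.4.2 is ED visits and hospitalizations, which the chart captures. The study is described as minimal risk and has a DSMB.

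Much of this stands. A reader might infer that late events are lost, or that up to 62.5% of participation is uncovered; the documents do not support that. What is missing is scheduled questioning, and the remaining routes are either unprompted or confined to asthma-related utilization. The reply does not remove the conflict, since Table 1 cannot settle it and a coordinator working from the lists would not ask.

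A reader might also infer that any harms comparison is biased against the intervention. That goes too far: no such comparison is specified, S+ v S- is untouched, the month 9 to 12 gap affects both arms, and the P+ v P- effect vanishes with full recall. Dividing 90% by an assumed 50% for the whole first quarter, to get 1.80, would also be wrong, because the arms are asked at the same time after week 6.

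**Conclusion.** The inconsistency is established from the text and should be corrected. Under the lists there is no scheduled adverse event question after month 9 in either arm, and P+ is asked 7 times against 4. A P+ v P- tabulation of solicited events is liable to over-count P+. In the illustration the 12-month ratio runs from 1.00 with full recall to 1.08 at a 3-month half-life and 1.45 at half a month. These values rest on assumed recall and equal true rates, so they show direction and range only and do not estimate the bias in this trial.

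Nothing here alters the primary or secondary efficacy analyses. The stake is the completeness of safety reporting and whether harms by group can be interpreted.

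**What to change.** - Reconcile section 5.5 and the synopsis with sections 4.2.3, 4.3.6 and 4.3.7: add the adverse event item at Visit 5, Home Visit 4 and Visit 6, and add an adverse event row to Table 1. State whether Visit 6 applies to P-.
- At Visits 2 to 5, ask every child in both arms about the whole interval since the previous common visit (for Visit 2, since enrollment), whether or not an event was already reported at a home visit.
- State in the SAP that any P+ v P- adverse event table uses those common-visit answers. The look-back and the lag are then the same in both arms.
- Report every event, including those found at home visits, in a full listing by arm that shows the source.
- Do not drop P+ home-visit events from the comparison unless this equal look-back is in place.

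The cost is a short protocol amendment, one question at visits already scheduled, and a sentence in the SAP. The small downside is one repeated question for P+ families at Visit 2.

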### 6 STATISTICAL CONSIDERATIONS

## **6.1 Primary Endpoint**

The primary endpoint is the difference in asthma control between the intervention and the control group.

# 6.2 Secondary Endpoints

Secondary endpoints will include the following:

- The change in asthma symptom days between the intervention and the control group
- The change in school absences between the intervention and the control group
- The change in ED visits and inpatient hospitalizations for an asthma-related cause between the intervention and the control group.

#### 6.3 Statistical Methods

#### 6.3.1 Baseline Data

Baseline and demographic characteristics will be summarized by standard descriptive summaries (e.g. means and standard deviations for continuous variables such as age and percentages for categorical variables such as gender).

### 6.3.2 Efficacy Analysis

The primary analysis will be based on an intention to treat approach and will include all subjects randomized at Study Visit 1. The primary efficacy endpoint will be the change in asthma control between Study Visit 1 and Study Visit 5. Secondary efficacy endpoints will include the change in asthma symptom days and school absences between Study Visit 1 and Study Visit 5.

### 6.3.3 Subgroup Analysis: Mediator and Moderator Variables

Baseline variables including asthma control, BMI, school type (public/charter) and demographic characteristics which may serve as moderators of intervention effectiveness will be evaluated through subgroup analyses. These variables will be used to identify subgroups of children that may be more likely to benefit from the study interventions. Mediator variables such as communication between school and primary care and level of participation in school-based asthma therapy will be evaluated to better understand the mechanism of effect of the intervention on the study's primary outcomes.

## 6.4 Sample Size and Power

The factorial design has enhanced statistical power and can handle cluster randomization of schools. Our statistical methods will also estimate variation in the effect across schools over time. First, linear mixed effects models with random intercepts and slopes for school, and fixed effects for the school-level intervention, time, and time-by-intervention interaction (the estimate of interest) will be applied. Likewise, the main effect for the child-level intervention and a time\*intervention interaction term will be included in the model, and variation across multiple measurements on a child within a school will be accounted for by child-level random effects. Second, marginal models using generalized estimating equations will produce robust estimates that adjust for clustering at the school level. Third, assumption-free, randomization-test-based (permutation test) methods do not rely on assumptions of parametric models. We will use conventional levels of statistical significance (p=0.05) for all pre-specified comparisons for these aims and shall report all results to confirm consistency of findings and their robustness to model specifications. Variability of the intervention effect across schools will reflect consistency of intervention effects and thus generalizability in new settings. Both mixed effects models and permutation-test methods will estimate variance components. All contrasts noted in specific Aims 1a through 1d are handled with the same modeling specifications. This approach will also be used to account for change over time across schools, and to assess sustainability of the proposed interventions.

Missing data on covariates will be handled using formal multiple imputation as needed. The proposed mixed effects models make limited assumptions of "missing at random" (MAR). To the extent that children are lost to follow-up, we shall include in our models covariates that are associated with the probability of dropout to limit confounding by dropout. We anticipate no school withdrawals, but in case of loss, we will use all data collected until time of dropout. The primary analysis will be "as randomized" (also called intention to treat). Reporting will follow the CONSORT guidelines for randomized studies and cluster randomized designs.

All power estimates are based on custom programmed simulations. The pre-specified contrasts from specific aims 1a, 1b, and 1c, appear in Table 2. All power estimates represent changes over time in the primary outcome (asthma control) in units of standard deviation of change. For translation into clinical terms, the minimally important difference (MID) for children on the Juniper's Asthma Control Questionnaire is 0.5 standard deviation units, which equates to 0.4 units on the questionnaire scale (for children ages 6 to 17 years). Estimates assumed a modest degree of variation in outcomes across schools, which equates to clustering of children within schools. For an overall effect size of 0.5 standard deviation units, we assumed that individual schools would vary from no effect (0.0) to a large effect (1.0 sd units). This degree of variation corresponds to a random cluster (school) effect of 0.025 sd units, and an intraclass correlation coefficient (ICC) of 0.06. With an average of 28 children per school, this variability equates to a design effect (variance inflation factor) of about 2.5. As the table shows, the contrasts for the primary care intervention are powerful to show even small effects, because they are within-cluster comparisons and therefore are influenced if at all only slightly by clustering of children within schools. Across school contrasts, of the effects of the school intervention, remain powerful for MID changes.

**Table 2. Power for Contrasts of Interest** 

Specific Aim	Contrast	Contrast (Table cell)	Stipulated Effect size(sd)			Estimated Power
			Р	S	P,S	
1a	S+ v S-	a,b vs c,d	0.5	0.5	0.1	0.90
1a	P+ v P-	a,c vs b,d	0.25	0.25	0.1	0.95
1b	S+P+ v S-P+	a vs c	0.5	0.5	0.1	0.95
1b	S+P+ v S+P-	a vs b	0.35	0.5	0.0	0.88
1b	S- P+ v S+P-	b vs c	0.75	0.25	0.0	0.92
1c	S+P+ v S-P-	a vs d	0.25	0.25	0.1	0.96
1c	S- P+ v S-P-	c vs d	0.35	0.5	0.0	0.90
1c	S+P- v S-P-	b vs d	0.5	0.5	0.1	0.90
20%	Subgroup					
2a	S+ v S-	a,b, vs c,d	0.5	0.6	0.1	0.83
2a	P+ v P-	a,c vs b,d	0.5	0.6	0.1	0.88

P=Primary care effect; S=School Effect; PS= interaction; "+" = , "-" = control

Cells e, f are not included in this table for simplicity and to be conservative.

### 6.5 Interim Analysis

Interim efficacy or safety analyses not expected.

# 7 STUDY MEDICATION (STUDY DEVICE OR OTHER STUDY INTERVENTION)

### 7.1 Description

All medication taken by participating children will be prescribed by their primary care provider.

#### 8 SAFETY MANAGEMENT

#### 8.1 Clinical Adverse Events

Clinical adverse events (AEs) will be monitored throughout the study.

# 8.2 Adverse Event Reporting

Since the study procedures are not greater than minimal risk, SAEs are not expected. If any unanticipated problems related to the research involving risks to subjects or others happen during the course of this study (including SAEs) they will be reported to the IRB in accordance with CHOP IRB SOP 408: Unanticipated Problems Involving Risks to Subjects. AEs that are not serious but that are notable and could involve risks to subjects will be summarized in narrative or other format and submitted to the IRB at the time of continuing review.

### 9 STUDY ADMINISTRATION

### 9.1 Treatment Assignment Methods

### 9.1.1 Randomization

Allocation concealment will be preserved by randomly permuted block. This randomization will produce a 2-by-2 factorial design, partly clustered (by school).

TABLE 3		Child-Level			
		Intervention			
		P+	P-		
School	S+	А	В		
Level	S-	С	D		
Intervention	none	E	F		

The proposed design results in 6 groups of children. Children who do not attend a participating school will be randomized to the primary care CHW (child-level) intervention or not (groups E and F) and will be followed for the duration of the study. The cells A,B,C will permit comparison of any of the 3 combinations of school and child intervention against the group that has neither (D), and will permit marginal analysis of the effect of the school intervention (A+B vs C+D), and the marginal effect of the primary care intervention

(A+C+E vs B+D+F). We will collect baseline data on children and then follow schools and children over time. This design avoids contamination and interference through cluster randomization, but benefits from added power of a longitudinal analysis. It permits estimation (and testing) of interaction between the school and individual interventions. All randomization schemes will be prepared by the project statistical team and implemented using opaque sealed envelopes or a similar process electronically via REDCap.

### 9.1.2 Blinding

The PI will be blinded to the intervention/treatment group to the extent possible.

### 9.1.3 Unblinding

Unblinding will occur if there is an adverse event that warrants investigation or if the DSMB instructs the PI to become unblinded.

### 9.2 Data Collection and Management

For the study intervention, data will be collected, accessed and stored by the CHWs and study research team. Any paper forms will be stored in a locked cabinets in the Community Asthma Prevention Program's (CAPP) badge-only accessible suite. Data collected using REDCap is accessible only by the CHWs and research study staff. Designated school administrators (i.e. principal), the school nurse and the child's primary care provider will only have access to participant health care information necessary to conduct asthma management in the schools and primary care office, but none of the research data collected by the CHWs and study staff. Information will be kept confidential under HIPPA guidelines and Institutional policies.

We will implement the following:

- A master list containing PHI and subject ID number separate from data forms (paper and electronic) that have only a study ID number.
- The master list and any other files with be password protected and kept on a secure CHOP computer to prevent double enrollments.

CHOP's Department of Biomedical and Health Informatics (DBHi) will work with the research team to extract variables from the EHR, and also provide support for the design and use of the REDCap database.

